12.6.5 Physical Examinations

Full physical examinations will include an evaluation of the head and neck as well as cardiovascular, respiratory, gastrointestinal, neurological, dermatological, and musculoskeletal systems (Appendix 7 and Appendix 8). Abbreviated physical examinations will be performed based on patient/caregiver-reported symptoms (Appendix 7 and Appendix 8).

All physical examination results will be presented in a data listing.

12.6.6 Electrocardiograms

Triplicate 12-lead electrocardiogram (ECG) will be obtained after the patient has been resting for at least 5 minutes. For clinically significant ECG findings, a follow-up ECG should be performed within 24 hours and again 7 days later to ensure the abnormality is not worsening. Follow-up 12-lead ECGs may be performed locally, with the results sent to the Investigator.

Heart rate, PR interval, RR interval, QRS duration, QT interval, QTcB interval, QTcF interval as well as investigator's interpretation of the ECG will be collected in the eCRF. All ECG results along with the investigator's interpretation, including the average of triplicate measurements at each timepoint, will be presented in data listings.

QTcF values will be presented with the implementation of corrections (i.e., Fridericia's) as defined in International Council for Harmonisation (ICH) Guidelines E14. Frequency count and percentage will be tabulated by the following categories. This summary will also be provided for each of age groups (6 to <10 years; 10 to <20 years and 20 to ≤65 years) and sex for the Double-Blind Treatment Phase. The same summaries by age groups and/or sex may be repeated for the OLE Phase.

Absolute QT interval corrected for heart rate based on Fridericia's formula (QTcF) prolongation:

- QTcF interval >442 ms (6 to <10 years old)
- QTcF interval >439 ms (10 to <20 years old)
- QTcF interval >450 ms (male, 20 to ≤65 years)
- QTcF interval >470 ms (female, 20 to \leq 65 years)
- QTcF interval >500 ms (regardless of age and gender)

Change from Baseline in QTcF interval:

- QTcF interval increases from Baseline 30-60 ms
- QTcF interval increases from Baseline >60 ms

In addition, potential QT prolongations will be categorized as:

- PR interval >300 msec
- QRS duration >140 msec
- PR interval increase from Baseline >50%
- QRS duration increase from Baseline >40%
- HR increase >65% from Baseline
- HR decrease >40% from Baseline

The actual values and change from Baseline values at each time point will be summarized for the safety populations. The overall interpretation will also be summarized by timepoint as well as the worst post-baseline.

12.6.7 Columbia-Suicide Severity Rating Scale (C-SSRS)

The Columbia-Suicide Severity Rating Scale (C-SSRS) scale is composed of items answered

The C-SSRS also includes a suicidal ideation intensity rating from

Results of C-SSRS will be provided in listings only.

12.6.8 Anxiety, Depression, And Mood Scale (ADAMS)

[figure not shown]

Table 14: Scoring for each Domain

Manic/ Hyperactive Behavior	Depressed Mood	Social Avoidance	General Anxiety	Obsessive/ Compulsive Behavior

Results of ADAMS and change from Baseline will be summarized at each nominal visit and provided in data listings. This summary will also be provided for each of age groups (6 to <12 years; 12 to <18 years and 18 years or older) for the Double-Blind Treatment Phase. The same summary by age group may be repeated for the OLE Phase.

The following data will also be summarized (from the Baseline assessment):

- Background of the individual being rated:
 - Level of intellectual disability
 - Living situation
 - Disabilities
- Information for the individual completing the form:
 - Relationship with the individual
 - Length of relationship
 - Setting of contact

Appendix 1 Glossary of Abbreviations

Glossary of Abbreviations:				
ABC-2	Aberrant Behavior Checklist, Second Edition			
ADAMS	Anxiety, Depression, and Mood Scale			
AE	Adverse event			
ANCOVA	Analysis of covariance			
AUC	Area under the plasma concentration-time curve			
AUC _{last}	AUC from time 0 to the last collection time			
BLQ	Below the limit of quantification			
CaGI-S	Caregiver Global Impression of Severity			
CGI-S	Clinical Global Impression of Severity			
CHW	Cui, Hung, Wang			
C _{max}	Maximum observed plasma concentration			
COVID-19	Coronavirus Disease 2019			
CRF	Case Report Form			
C-SSRS	Columbia-Suicide Severity Rating Scale			
CV%	Coefficient of variation			
CYP	Cytochrome P450			
ECG	Electrocardiogram, electrocardiography			
EDS	Excessive daytime sleepiness			
EOT	End of Treatment			
ESS-CHAD	Epworth Sleepiness Scale for Children and Adolescents			
ET	Early Termination			
FDA	Food and Drug Administration			
FSZQ	Food Safe Zone Questionnaire			
GCP	Good Clinical Practice			
H_1	Histamine 1			
HQ-CT	Hyperphagia Questionnaire for Clinical Trials			
ICH	International Council for Harmonisation			
inf	infinity			
IXRS	Interactive voice/web response system			
LLOQ	Lower limit of quantification			
LS	Least square			

MERS-PWS	Montefiore-Einstein Rigidity Scale – Prader-Willi Syndrome
MI	Multiple Imputations
mITT	Modified Intent-to-Treat
MMRM	Mixed effect model repeated measures
MSL	Mean sleep latency
MSLT	Multiple sleep latency test
NIH	National Institutes of Health
OLE	Open-Label Extension
PK	Pharmacokinetic(s)
PSG	Polysomnography
PWS	Prader-Willi syndrome
QTcF	QT interval corrected for heart rate based on Fridericia's formula
RT	Reaction time
SAE	Serious adverse event
SAP	Statistical analysis plan
SD	Standard deviation
SE	Standard Error
SI	International System of Units
TEAE	Treatment-emergent adverse event
t _{max}	Time to observed maximum plasma concentration
US	United States (of America)
WHO	World Health Organization
WNL	WinNonLin software
ZBI-22	22-item Zarit Burden Interview

Appendix 2 Prior and Concomitant Medication Start/Stop Date Imputation

Imputation Rules for Partial Dates (D = day, M = month, Y = year)

Parameter	Missing	Additional Conditions	Imputation
Start date for con meds	D only	M and Y same as M and Y of first dose of study drug	Date of first dose of study drug
		M and/or Y not same as date of first dose of study drug	First day of month
	M and D	Y same as Y of first dose of study drug	Date of first dose of study drug
		Y not same as Y of first dose of study drug	Use Jan 01 of Y
	M, D, and Y	None - date completely missing	Day prior to date of first dose of study drug
Stop date for con meds	D only	M and Y same as M and Y of last dose of study drug	Date of last dose of study drug
		M and/or Y not same as date of last dose of study drug	Last day of month
	M and D	Y same as Y of last dose of study drug	Date of last dose of study drug
		Y not same as Y of last dose of study drug	Use Dec 31 of Y
	M, D, and Y	None - date completely missing and NOT ongoing	Date of last dose of study drug

Note: In all cases, if an estimated start date is after a complete stop date, use the first day of the stop date month.

Similarly, if the estimated stop date is before a complete or imputed start date, use the last day of the start day month.

Appendix 3 Example of Prohibited Medications

Examples of medications that are strong CYP2D6 inhibitors, strong CYP3A4 inducers, medications that prolong QT interval, and centrally acting H₁ receptor antagonists.

Medication Type	Example
Strong CYP2D6 inhibitors	paroxetine, fluoxetine, bupropion, metoclopramide, and quinidine.
Strong CYP3A4 inducers	rifampin, carbamazepine, phenytoin, dexamethasone, ethosuximide, griseofulvin, primidone, progesterone, rifabutin, nafcillin, nelfinavir, nevirapine, phenobarbital, phenylbutazone, St John's wort, sulfadimidine, sulfinpyrazone, and troglitazone
Medications that prolong QT interval	Class 1A antiarrhythmics: quinidine, procainamide, disopyramide;
	Class 3 antiarrhythmics : amiodarone, sotalol;
	Antipsychotics: ziprasidone, chlorpromazine, thioridazine;
	Antibiotics: moxifloxacin
H ₁ receptor antagonists	pheniramine maleate, diphenhydramine, promethazine (anti- histamines) imipramine, clomipramine, mirtazapine (tri or tetracyclic antidepressants
Opiates	
Investigational drugs (with the exception of diazoxide choline)	

CYP = cytochrome P450.

[figure not shown]
Note: Although Section 5.7.1 of the protocol mentions carbetocin and oxytocin as being permitted, they were in fact prohibited due to being investigational drugs (Section 5.7.2 in the protocol).

The use of strong CYP2D6 inhibitors or strong CYP3A4 inducers is not permitted during the Double-Blind Treatment Phase of the study, and if being used, should be discontinued at Screening; washout of 5 half-lives or 1 week (whichever is longer) of these medications is required prior to enrollment and initiating study drug. These medications are allowed during the OLE Phase of the study, but adjustment of the dose of pitolisant may be required.

Concomitant use of centrally acting H₁ receptor antagonists is not permitted during the Double-Blind Treatment Phase of the study (requires a washout of 5 half-lives or 1 week, whichever is longer, prior to randomization). Although not prohibited during the OLE Phase of the study, use of these medications should be avoided and, if needed, will require consultation with the Medical Monitor.

Appendix 4 SAS Sample Code

Below are examples of code for the data imputations and inferential statistics described in the SAP.

MMRM:

MIAnalyzed (for the MMRM):

ANCOVA:

Appendix 5 Adverse Event Start/Stop Date Imputation

Imputation Rules for Partial Dates (D = day, M = month, Y = year)

Parameter	Missing	Additional Conditions	Imputation
Start date for AEs	D	M and Y same as M and Y of first dose of study drug	Date of first dose of study drug
		M and/or Y not same as date of first dose of study drug	First day of month
	D and M	Y same as Y of first dose of study drug	Date of first dose of study drug
		Y prior to Y of first dose of study drug but same as Y of screening date	Date of screening date
	D, M, Y	None - date completely missing	Date of first dose of study drug
Stop date for AEs	D	M and Y same as M and Y of last dose of study drug	Date of last dose of study drug
		M and/or Y not same as date of last dose of study drug	Use last day of month
	D and M	Y same as Y of last dose of study drug	Date of last dose of study drug
		Y not same as Y of last dose of study drug	Use Dec 31
	D, M, Y	None - date completely missing	No imputation, but assume ongoing

Note: In all cases, if an estimated start date is after a complete stop date, use the first day of the stop date month.

Similarly, if the estimated stop date is before a complete or imputed start date, use the last day of the start day month.

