9.2 Study Day Windows

For each patient there will be a Screening period, a Double-Blind Treatment Phase, and an OLE Phase (optional).

The study day for data collected prior to first dose, will be calculated as visit date – first dose date. For data collected after the first dose, the study day will be calculated as visit/assessment date – first dose date + 1. The first dose date refers to the date the study drug was taken for the first time, i.e., at the beginning of the Double-Blind Treatment Phase.

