For patients who opt to continue in the OLE Phase of the study, only AEs starting strictly before the first dose in the OLE Phase will be summarized for the Double-Blind Treatment Phase, and any AEs that started on or after the first dose of treatment in the OLE Phase and up to 30 days after the last dose of treatment in the Double-Blind Treatment Phase will be included in a separate listing (for the OLE Phase reporting); these AEs will be included in the OLE Phase summaries. A listing of all the AEs that were ongoing (i.e. that are ongoing or have a stop date after the first dose of treatment in the OLE Phase) at the end of the Double-Blind Treatment Phase will be included in the OLE Phase reporting to capture additional information for those AEs (such as end date and potential treatments) and patients will not necessarily be on the same treatment as what they were randomized to in the Double-Blind Treatment Phase.

For the OLE Phase, the same data summaries and listings will be produced. The data will be tabulated for overall and by period

. Calculations for AE start and stop dates are detailed in Appendix 5.

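### SAP Appendix 5 has no open-label anchor for partial adverse event start dates, so some open-label events are dated into the double-blind phase and one kind of date has no rule

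*SAP*

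**What the plan says.** SAP Appendix 5 completes a partial AE start date as follows:

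- Day missing, month and year those of the first dose: date of first dose.
- Day missing, "M and/or Y not same as date of first dose of study drug": first day of the reported month.
- Day and month missing, "Y same as Y of first dose of study drug": date of first dose.
- Day and month missing, "Y prior to Y of first dose of study drug but same as Y of screening date": screening date.
- "None - date completely missing": date of first dose.

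A note under the table adds: "In all cases, if an estimated start date is after a complete stop date, use the first day of the stop date month".

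The appendix does not define first dose for itself. SAP 9.2 does, for study-day purposes: "the date the study drug was taken for the first time, i.e., at the beginning of the Double-Blind Treatment Phase". No row mentions the first OLE dose. SAP 12.6.1 ends its account of OLE AE reporting by referring start and stop dates to Appendix 5, and no separate OLE rule is given.

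Phase then follows from the start date. For patients who continue into the OLE, SAP 12.6.1 says that "only AEs starting strictly before the first dose in the OLE Phase will be summarized for the Double-Blind Treatment Phase". SAP 9.6 defines the double-blind data cut in the same way. An AE is treatment-emergent in the OLE if it starts on or after the first OLE dose (SAP 12.6.1). Safety tables use the treatment actually received (SAP 10.0).

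**The concern.** Dating an unknown start to the first dose is a cautious choice in a one-phase study, because it makes the event treatment-emergent. This study has two phases in one database, and the start date alone decides the phase. Pulling an open-label event back to the first double-blind dose removes it from the OLE treatment-emergent summaries. It may also place the event under the patient's double-blind treatment, which for about a third of patients is placebo. An AE that arose on open-label pitolisant could then appear in a placebo column.

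**Working it through.** The plan states no figure on this point, so the check applies the written rules.

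**Inputs.** First double-blind dose = Day 1 (SAP 9.2). First OLE dose = Day 78 (SAP 8.1), that is, Day 1 + 77 days. Start-date rows from Appendix 5. Phase rule: imputed start before first OLE dose = double-blind; otherwise OLE.

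**Example.** First dose 10 March 2021, so first OLE dose 26 May 2021 (21 + 30 + 26 = 77 days). For events that truly began in the OLE:

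- Recorded as May 2021 (true start 26 to 31 May): imputed 1 May, so double-blind.
- Recorded as June 2021: imputed 1 June, so OLE. This is correct.
- Recorded as 2021: imputed 10 March, so double-blind.
- Recorded as 2022: no row applies.
- No date at all: imputed 10 March, so double-blind.

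**The note under the table.** It acts only when the imputed start is later than a complete stop date, and it then moves the start earlier. It cannot bring an event back into the OLE.

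**Size by type of missingness.** The rules were run for every first-dose date from 2021 to 2024, with one true OLE event on each study day in the range and the note not triggered. Shares of true OLE events:

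| True start | Day missing: placed in double-blind | Day and month missing: placed in double-blind | Day and month missing: no rule | Fully missing: placed in double-blind |
|---|---|---|---|---|
| Days 78–84 | 86.9% | 78.1% | 21.9% | 100% |
| Days 78–98 | 63.9% | 76.2% | 23.8% | 100% |
| Days 78–189 | 13.2% | 63.7% | 36.3% | 100% |
| Days 78–369 | 5.0% | 39.1% | 60.9% | 100% |
| Days 78–549 | 3.1% | 24.2% | 75.8% | 100% |
| Days 99–369 | 0.5% | 36.2% | 63.8% | 100% |

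**Hand check of the day-missing column.** Misplaced events lie between the first OLE dose and the end of that month, and there are none if dosing starts on the 1st. With an average month of 365.25/12 = 30.4 days, that is (30.4 − 1)/2 = 14.7 days on average. Days 78–369 are 292 days: 14.7/292 = 5.0%. Days 78–549 are 472 days: 14.7/472 = 3.1%. Both agree with the table.

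The day-missing row therefore matters mainly in the OLE titration period (Days 78–98), when patients who had been on placebo first take pitolisant. The fully-missing and same-year rows cause misplacement well beyond that period.

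**The case against.** The case for leaving the appendix alone has real substance.

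- **Dense contact.** AEs are reviewed at Day 77, Day 85, Day 92 and Day 99 (protocol schedules of assessments). An unknown start day is least likely in the weeks where the day-missing row does harm. This stands, and is one reason to expect few cases.
- **Unknown day in general.** A reader might infer that any OLE event with an unknown day moves to the double-blind phase. It does not; only the calendar month of OLE entry is affected. Nor is every such event in that month misplaced. In the example, 25 days of May precede the first OLE dose, and an event that began on one of them gets the right phase from 1 May.
- **Arm.** A reader might infer that misplaced events go to the randomised arm. Safety tables use treatment received (SAP 10.0), though a patient treated with placebo is still counted under placebo.
- **Direction.** A reader might infer that pitolisant AEs are understated throughout. The OLE summaries do lose events. In the double-blind tables, however, randomisation is 1:1:1, so about two thirds of patients are in active arms, and a shift there raises an active-arm count.
- **Disappearance.** A reader might infer that events recorded after the double-blind lock vanish from both reports. SAP 12.6.1 requires, in the OLE reporting, a listing of AEs that are ongoing or stop after the first OLE dose, and a back-dated OLE event would meet that test in all but same-day cases. It remains visible, though outside the OLE incidence tables.
- **Redaction.** The text on OLE tabulation by period is blacked out just before the pointer to Appendix 5, so part of the OLE handling cannot be seen. The appendix itself is legible and has no OLE row.

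These points limit the effect. They do not change what the written rows do to fully missing, same-year and entry-month dates.

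**Conclusion.** The point holds as a low-impact defect. For three kinds of true OLE event the written rules give the wrong phase: start date fully missing; only a year known, equal to the first-dose year; and only the day missing, with onset after OLE dosing in the month of OLE entry (unless dosing began on the 1st). For a fourth kind, a year-only date later than the first-dose year, there is no rule.

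The three misplaced kinds leave the OLE treatment-emergent summaries. They enter the double-blind tables only if already in the database at the double-blind cut. That is possible for early enrollees, because reporting waits until all patients have finished or left the double-blind phase (SAP 12.4.1). The bias there depends on the arm.

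The percentages assume an even spread of events, OLE dosing from Day 78, and first dose in Appendix 5 meaning what SAP 9.2 says. They are shares of events with that type of missing date, not of all AEs. The number of partial dates is not given and is probably small, and the safety analysis is descriptive only (SAP 12.6).

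**What to change.** Add OLE rows to SAP Appendix 5:

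1. The rows apply to an AE first recorded at a contact after the first OLE dose, whose partial date is compatible with a start on or after that dose, and whose stop date, if known, is not before it. For such an AE, impute the later of the first OLE dose date and the first day of the reported month or year.
2. If the start date is fully missing and the other conditions in 1 hold, impute the first OLE dose date.
3. For a year-only date after the first-dose year, impute 1 January of that year, or the first OLE dose date if that is later and the conditions in 1 hold.
4. List every AE whose phase depends on an imputed date.

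The cost is a few table rows and one listing. The rule needs the contact at which each AE was first recorded, which Appendix 5 does not use at present. The downside is that an occasional double-blind event reported late would move to the OLE and leave the placebo-controlled comparison; the listing in 4 lets a reader see each case. Protocol 1.3.2 describes the double-blind phase as completed, so the new rows would act mainly on the separate OLE report planned in SAP 9.6. For the double-blind tables, a check for affected events is enough.

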Appendix 6 Clinical Laboratory Tests

-Amphetamines/stimulants^a

-Barbiturates -Benzodiazepines -Cocaine metabolites

-Opiates

-Tetrahydrocannabinol

-Phencyclidine

Urinalysis

-Specific gravity

-pH -Blood -Glucose -Protein

-Leukocyte esterase

-Ketones -Bilirubin -Nitrites -Casts -Crystals -Erythrocytes

-Renal tubular epithelial cells

-WBCs -Bacteria

Serum Drug Screen

-Cannabidiol

Pregnancy Screen (FCBP only)

-Serum (at Screening only) -Urine (as scheduled after

screening)

-Albumin

-Alkaline phosphatase -Alanine aminotransferase -Aspartate aminotransferase

-Blood urea nitrogen

-Calcium

-Chloride -Creatinine

-Creatine kinase

-Glucose

-High-density lipoprotein -Low-density lipoprotein

-Phosphorus -Potassium -Sodium

-Total bilirubin -Direct bilirubin -Total cholesterol -Total protein -Triglycerides

-Uric acid -Ghrelin^b

Hematology (4.0 mL blood sample)

-Complete blood count, including platelet count and WBC count

with differential -Hemoglobin -Hematocrit

-HbA1c

Abbreviations: FCBP = female of child-bearing potential; HbA1c = hemoglobin A1c; WBC = white blood cell

Note: Parameters will be assessed at study visits as detailed in the Schedule of Assessments for the Double-Blind Treatment Phase and the Schedule of Assessments for the OLE Phase.

^a Stimulants are tested in the Double-Blind Treatment Phase only.

b Acylated and unacylated ghrelin; patient must be fasting. Blood sample for ghrelin measurement may be taken at the same time as clinical laboratory test sample.

Appendix 7 Schedule of Assessments Double-Blind Treatment Phase

	Screening/Baseline ^a (Maximum 45 days)		Double-Blind Treatment Phase (11 Weeks)										
			Titration Period (3 weeks) ^b Day 1 to 21			Stable Dose Period (8 weeks) ^e Day 22 to 77							
Visit/TC Study Day	Screening VISIT 1 Day -45 to -2	Baseline VISIT 2 Day -1	Day 1 ^b (+2 days)	TC 1 Day 8 (±3 days)	TC 2 Day 15 (±3 days)	VISIT 3 ^d Day 22 (±3 day)	TC 3 Day 29 (±3 days)	TC 4 Day 36 (±3 days)	VISIT 4 ^d Day 50 (±3 days)	TC 5 Day 57 (±3 days)	EOT*/ETf VISIT 5 Day 77 (±3 days)	Safety F-Up TCs ^g	Unsch visits ^h
Informed consent	X												
Assess/confirm eligibility	x	X											
Demographics	X												
Medical history	X	X											
Pregnancy test (FCBP) ⁱ	X	X				x			х		X		
Urine drug screen ^j	x	х									х		
Physical examination ^k	х	х				х			х		х		
Body weight ^l	X	X				X			Х		X		X
Height ^l	X										X		X
Vital signs ^m	X	X				X			X		X		X
12-lead ECG (in triplicate) ⁿ	x	X				x			х		X		
C-SSRS°	х	Х		X	Х	X	X	X	X	Х	Х	X	
ADAMS	х	X				X	X	X	X	X	X	X	
Clinical laboratory tests ^p	x	\mathbf{X}^{q}				X			х		$\mathbf{X}^{ ext{q}}$		

	Screening/Ba (Maximum 4		Double-Blind Treatment Phase (11 Weeks)										
				ration Per (3 weeks) ^b Day 1 to 2	•	Stable Dose Period (8 weeks) ^c Day 22 to 77							
Visit/TC Study Day	Screening VISIT 1 Day -45 to -2	Baseline VISIT 2 Day -1	Day 1 ^b (+2 days)	TC 1 Day 8 (±3 days)	TC 2 Day 15 (±3 days)	VISIT 3 ^d Day 22 (±3 day)	TC 3 Day 29 (±3 days)	TC 4 Day 36 (±3 days)	VISIT 4 ^d Day 50 (±3 days)	TC 5 Day 57 (±3 days)	EOT*/ETf VISIT 5 Day 77 (±3 days)	Safety F-Up TCs ^g	Unsch visits ^h
Ghrelin measurements		\mathbf{X}^{q}									\mathbf{X}^{q}		
Genetic testing ^r	X												
Dispense study diary ^s	х												
Adverse events ^t	X	X		X	X	X	X	X	X	X	X	X	X
Concomitant medications	X	X		X	X	X	X	x	X	х	X	х	X
Randomization		X											
Dispense study drug ^u		X				X			X		X		
Administer/titrate study drug			Xb	X ^b	Xb	$\longleftarrow \qquad \qquad X_c \qquad \longrightarrow \qquad$					\longrightarrow		
Study drug compliance/ accountability				х	X	х	x	х	X	x	x		x
Blood sample for PK						X ^v			Xw		X ^v		
ESS-CHAD (parent/caregiver version)	х	х				х			х		х		
CaGI-S (of EDS)		X				X			X		X		

	Screening/Baseline ^a (Maximum 45 days)		Double-Blind Treatment Phase (11 Weeks)										
			Titration Period (3 weeks) ^b Day 1 to 21			Stable Dose Period (8 weeks) ^e Day 22 to 77							
Visit/TC Study Day	Screening VISIT 1 Day -45 to -2	Baseline VISIT 2 Day -1	Day 1 ^b (+2 days)	TC 1 Day 8 (±3 days)	TC 2 Day 15 (±3 days)	VISIT 3 ^d Day 22 (±3 day)	TC 3 Day 29 (±3 days)	TC 4 Day 36 (±3 days)	VISIT 4 ^d Day 50 (±3 days)	TC 5 Day 57 (±3 days)	EOT*/ETf VISIT 5 Day 77 (±3 days)	Safety F-Up TCs ^g	Unsch visits ^h
CGI-S (overall clinical status related to PWS)		x				х			х		x		
ABC-2		X				X			Х		X		
MERS-PWS		X				X			X		X		
Cogstate Detection	Xx	X							X		X		
Cogstate Identification	X ^x	X							х		X		
Cogstate One Back	Xx	X							x		x		
ZBI-22		\mathbf{X}^{bb}				X			X		X		
HQ-CT		X				X			X		X		
FSZQ		X				X			X		X		

Abbreviations: ABC-2 = Aberrant Behavior Checklist, Second Edition; ADAMS = Anxiety, Depression, and Mood Scale; AE = adverse event; CaGI-S = Caregiver Global Impression of Severity; CDC = Centers for Disease Control and Prevention; CGI-S = Clinical Global Impression of Severity; C-SSRS = Columbia-Suicide Severity Rating Scale; ECG = electrocardiogram; EDS = excessive daytime sleepiness; EOT = end of treatment; ESS-CHAD = Epworth Sleepiness Scale for Children and Adolescents; ET = early termination; FCBP = female of child-bearing potential; FSZQ = Food Safe Zone Questionnaire; F-Up = follow-up; HbA1c = hemoglobin A1c; HQ-CT = Hyperphagia Questionnaire for Clinical Trials; MERS-PWS = Montefiore-Einstein Rigidity Scale - Prader-Willi Syndrome; OLE = Open-Label Extension; PK = pharmacokinetic(s); PWS = Prader-Willi syndrome; TC = telephone call; Unsch = unscheduled; ZBI-22 = 22-item Zarit Burden Interview.

a In the event that a portion of the Screening Visit is conducted remotely, specific procedures for both the Screening Visit and Baseline Visit will be conducted as detailed in Protocol Section 6.6.

b The 3-week Titration Period for the Double-Blind Treatment Phase will be from Days 1 to 21 (±3 days). Patients should take their first dose of study drug on the day after the Baseline Visit (Day 1), and study drug dose will be titrated on Day 8 and again on Day 15 (as appropriate based on randomized stable dose, Protocol Table 6); all patients will

be at their randomized stable dose of study drug by Day 15. Patients and/or their caregivers will receive TCs on Days 8 and 15 (±3 days) to assess for AEs and concomitant medication use, complete the C-SSRS, and review/confirm titration of study drug.

- ^c The 8-week Stable Dose Period in the Double-Blind Treatment Phase will be from Days 22 to 77 (±3 days); patients will take their last dose of blinded treatment on Day 77 ±3 days; study drug compliance will be monitored at TCs and study visits as detailed in Protocol Section 5.5.
- d In the event that Visit 3 and/or Visit 4 are conducted remotely, specific procedures will be conducted as detailed in Protocol Section 6.6.1.2.
- e Visit 5 (Day 77 ±3 days) is the EOT visit for the Double-Blind Treatment Phase. Eligible patients who enter the optional OLE Phase will be dispensed open-label pitolisant at this visit (Protocol Section 5.2.2); eligibility criteria must be confirmed before a patient can participate in the OLE Phase.
- f Patients who prematurely discontinue study drug are required to complete the ET Visit. Procedures to be performed are the same as for the EOT Visit (Protocol Section 7.3.3). Reasons for discontinuation must be recorded.
- g Patients who do not enter the optional OLE Phase will receive Safety Follow-up TCs from the study site 15 (±3 days) and 30 days (+3 days) after their final dose of blinded treatment to assess for AEs (including inquiries regarding signs and symptoms of arrhythmia, any other cardiac manifestations [e.g., syncope], and psychiatric events [e.g., suicidality, compulsive behavior, anxiety]) and concomitant medication use.
- h Unscheduled visits and assessments may be conducted by telephone or at an on-site study visit and should be performed if clinically indicated in the opinion of the Investigator (Protocol Section 7.6).
- ¹ Serum pregnancy test is to be performed at Screening and a urine pregnancy test is to be performed at all other visits, as indicated.
- ^j Urine drug screen as detailed in Protocol Table 9 is to be performed at the Screening Visit, Baseline Visit (on Visit 2), and at Visit 5 (Day 77).
- ^k Full physical examination is to be performed at the Screening Visit and Visit 5 (Day 77); abbreviated physical examination is to be performed at Visits 2, 3 and 4 (Protocol Section 6.5.2).
- ¹ Height and weight will be measured using standardized methods and recorded on a standardized growth chart (CDC Clinical Growth Charts).
- ^m Vital signs include blood pressure, heart rate, respiratory rate, and body temperature; patients should be resting for at least 5 minutes before measuring vital signs.
- ⁿ Perform 12-lead ECGs (in triplicate) after the patient has been resting for at least 5 minutes. Any clinically significant ECG reading should be promptly addressed by the Investigator as detailed in Protocol Section 6.5.4.
- o At Screening, suicidality is to be assessed through use of the Very Young Child/Cognitively Impaired—Lifetime Recent C-SSRS. (Protocol Appendix L). At all other study visits and TCs, suicidality will be assessed through use of the Very Young Child/Cognitively Impaired—Since Last Contact C-SSRS (Protocol Appendix M).
- ^p Clinical laboratory tests (serum chemistry, hematology, urinalysis) to include lipid profile and HbA1c (Protocol Table 9); laboratory tests may be repeated at unscheduled visits if necessary.
- ^q Ghrelin measurement is to be done fasting; clinical laboratory tests, including PK sample at Visit 5, may be done with the fasting ghrelin test.
- ^r Genetic testing will be provided by the Sponsor for patients who do not have documented genetic confirmation of PWS diagnosis based on the review of the patient's medical records.
- Patients will be dispensed a study diary containing a sleep diary section and a study drug dosing section at the Screening Visit (Protocol Appendix B).
- ¹ All AEs regardless of seriousness, severity, or causality will be collected from the time the patient/parent(s)/legal guardian(s) provides written informed consent/assent through 30 days (+3 days) after final dose of study drug (Safety Follow-up TCs, Protocol Section 7.5). At the Safety Follow-up TCs, AEs (including inquiries regarding signs and symptoms of arrhythmia, any other cardiac manifestations [e.g., syncope], and psychiatric events [e.g., suicidality, compulsive behavior, anxiety]) and concomitant medication use will be recorded, and the C-SSRS and ADAMS will be completed.
- ^u Patients will be instructed to take study drug once daily in the morning upon wakening; exception is on the morning of Visit 4, when study drug administration will be at the study site, with the timing of administration based on the PK sampling schedule. Patients will be instructed to record in the study drug dosing section of the study diary (with the assistance of their caregiver if needed) the number of tablets administered from each bottle daily (Protocol Appendix B); the time of study drug dosing will be recorded on the day before Study Visit 4.
- ^v Blood sample collection for PK analyses at Visit 3 and Visit 5 may be at any time after the morning dose of study drug and samples may be collected at the same time as the clinical laboratory sample (including the fasting ghrelin sample at Visit 5). Time of last dose of study drug and time of blood sample collection for PK analyses must be recorded.
- W Patients and/or their caregiver will be instructed to record in the study drug dosing section of the study diary the time of day that they take study drug on the day before Visit 4. On the day of Visit 4, patients will not take their daily dose of study drug before arriving at the study site. Study drug administration will be at the study site and timing will be based on the PK sampling schedule. At the study site, a blood sample for PK analyses will be collected before administration of the daily dose of study drug. The time

of study drug administration will be recorded. Blood sample collection for PK analyses will be at the following times after study drug administration: between 45 and 75 minutes after dosing, between 1.5 and 2.5 hours after dosing, between 3.0 and 4.0 hours after dosing, and between 5.0 and 6.0 hours after dosing. The time of each blood sample collection for PK analyses is to be recorded. The total volume of blood collected is not to exceed the maximal allowable of 3.0 mL/kg per day (Protocol Appendix A and Table 8).

^x To familiarize patients with the Cogstate Computerized Cognitive Test Battery, the tests are to be administered twice during Screening with a break of at least 15 minutes between battery administrations.

Assessments associated with on-site study visits during the Double-Blind Treatment Phase may be completed remotely, under the oversight of the Investigator, as detailed in Protocol Section 6.7.

